3.3.1 Inclusion Criteria for Randomization

In addition to meeting all criteria for enrollment, subjects must meet the following criterion **at time of randomization**: have P/F <200 with PEEP ≥8 cm H2O within 48h of randomization and within 14 days onset of COVID-19 symptoms. Alternatively, if ABG values are not available, P/F ratio <200 with PEEP ≥8 cm H2O; If ABG values are not available, the P/F ratio may be inferred from SpO2 values based on eTable 2 from Brown et al as long as following conditions are met:

- a. SpO2 values are 80-96%
- b. SpO2 is measured ≥10 min after any change in FIO2
- c. PEEP is ≥ 8 cm H2O
- d. the pulse oximeter waveform tracing is adequate
- e. the qualifying inferred P/F ratio is confirmed 1-6 hrs after the initial determination.

**eTable 2: Imputed PF ratio (cells) for combinations of SpO2 (rows) and FiO2 (columns)**

	0.30	0.35	0.40	0.45	0.50	0.55	0.60	0.65	0.70	0.75	0.80	0.85	0.90	0.95	1.00
80%	148	127	111	98	89	81	74	68	63	59	55	52	49	47	44
81%	151	129	113	101	91	82	76	70	65	60	57	53	50	48	45
82%	155	132	116	103	93	84	77	71	66	62	58	55	52	49	46
83%	158	136	119	106	95	86	79	73	68	63	59	56	53	50	47
84%	162	139	122	108	97	89	81	75	70	65	61	57	54	51	49
85%	167	143	125	111	100	91	83	77	71	67	63	59	56	53	50
86%	171	147	129	114	103	94	86	79	73	69	64	61	57	54	51
87%	177	151	132	118	106	96	88	81	76	71	66	62	59	56	53
88%	182	156	137	121	109	99	91	84	78	73	68	64	61	58	55
89%	189	162	141	126	113	103	94	87	81	75	71	67	63	60	57
90%	196	168	147	130	117	107	98	90	84	78	73	69	65	62	59
91%	203	174	153	136	122	111	102	94	87	81	76	72	68	64	61
92%	213	182	159	142	128	116	106	98	91	85	80	75	71	67	64
93%	223	191	168	149	134	122	112	103	96	89	84	79	74	71	67
94%	236	202	177	157	142	129	118	109	101	94	89	83	79	75	71
95%	252	216	189	168	151	138	126	116	108	101	95	89	84	80	76
96%	273	234	205	182	164	149	136	126	117	109	102	96	91	86	82

3.3.2 Randomization Procedures

Randomization will be performed by a macro-driven Excel spreadsheet (CHILL\_COVID\_Assignment\_Tool 1.0) stored on the UMB Microsoft OneDrive:

1. Select “CHILL\_COVID\_Assignment\_Tool 1.0,” click on the 3 vertical dots next to the file title, select “Open” and then on “Open in app.” If opening on a Mac, you will be given the option to enable macros. On a PC, you will have to manually enable macros once the file is open using the following steps:
  - a. Once the file is open, click on the “File” tab
  - b. Click on the “Enable Content” icon (upper left)
  - c. Click on “Advanced Options”
  - d. Select “Enable Content for this Session.”
  - e. The programs should the work.
2. On Sheet 1, Push “Push to Start” button
3. Enter your name from pulldown menu and push “Push to Start” button

4. Enter 3-digit study ID number from pulldown menu and push “Push to Start” button.
5. Re-enter 3-digit study ID number from pulldown menu and push “Push to Start” button.
6. If numbers do not match you will get an error message.
7. Otherwise enter 3-letter identifier and push “Push to Start” button.
8. Enter proning status from pulldown menu and push the “Confirm proning status, then push this button to get assignment” button.
9. The treatment assignment will be displayed in cell B12, all information will be entered along with date/time stamp on Sheet 2.
10. All data are automatically saved and the sheet locked so you just have to click on the close button.

If you make a mistake, make sure you the correct treatment assignment right away and let me know about the entry error so I can fix it. If you put in the wrong proning status, repeat with correct status and let me know so I can fix the error. If you entered wrong patient number or 3-letter code, use the treatment assignment provided and let me know so I can fix the error.

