
We have been approved for funding by Department of Defense (DoD) to support for a 4-year multicenter RCT of TH+NMB for 48h vs. standard of care with contract to be completed June 1, 2020 and with enrollment to begin in Fall of 2020. This study was designed prior to the onset of COVID-19, which is now the most common cause of ARDS and will likely continue to be in the Fall, 2020 and perhaps beyond. Therefore, it is important to decide whether patients with COVID-19 ARDS should be enrolled in our CHILL trial. Therefore, we will conduct a 20-patient pilot safety and feasibility trial of our CHILL TH+NMB treatment vs. control in COVID-19 patients with ARDS who meet the inclusion/exclusion criteria of our DoD-funded trial. The major objective of the proposed pilot trial is to determine whether it is safe and feasible to include patients with COVID-19 ARDS in our Phase IIb CHILL RCT of TH+NMB vs. control in patients with moderate to severe ARDS.

The pilot will be conducted at the University of Maryland Medical Center. To facilitate randomization within the inclusion window, we will consent and enroll based on partial fulfillment of randomization criteria and randomize once all criteria are met. Patients will be

eligible for enrollment when they have been diagnosed with COVID-19 by PCR, and have met all Berlin criteria for moderate to severe ARDS within the 48h inclusion window except the P/F ratio  $\leq 200$  but will not be randomized until P/F ratio (measured or imputed based on SpO2) is  $\leq 200$  (while on  $\geq 8$  cm H2O PEEP and  $\geq 0.6$  FiO2). We plan to randomize a total 20 patients over 4 months to hypothermia (core temperature 34°-35°C for 48h) plus NMB or usual temperature management. The primary outcome measures will be effectiveness of cooling in achieving and maintaining the target temperature and safety measures. Secondary outcomes will include 28-day ventilator-free days (VFDs), 28-day ICU-free days, oxygen saturation index (OSI), driving pressure, Sequential Organ Failure Assessment (SOFA) score, 60-day and 90-day survival, 90-day functional assessment, cognitive assessment at ICU and hospital discharge, and biomarkers of inflammation and lung injury. Since the nature of the intervention precludes blinding, all treatment and clinical decision making related to study outcomes will be protocolized and compliance with study protocols will be monitored.

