#### 2.2.1.2 Data Management Core Committee

Oversight for the Randomization and Data Management Core will reside within the DC. One or members of the clinical team will transcribe data from the patient study binder to an Excel form that summarizes the salient data for analysis to be performed by Drs. [name] and [name]. [name] will oversee generation of random assignments into the computer-based CHILL assignment tool, which records date and time, and name of investigator performing randomization.

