### 2.3.3 Coordinators

[name], RRT, MBA is the lead study coordinator and will oversee a coordinator team that includes [name] and a team of pulmonary and critical care fellows.

Responsibilities include:

1. Preparing and maintaining regulatory documents
2. Screening, enrollment, and randomization in all study units
3. Obtaining informed consent from participant or their legally authorized representatives (LAR).
4. Completion of case report forms (CRFs)
5. Identification of protocol deviations and their correction
6. Identification of AEs/SAEs and reporting
7. Obtaining and handling of biological specimens
8. Preparing data summaries for analysis

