#### Initial Patient Data Entry using on line screening tool:

1. Go to Microsoft 365 and log in using UMB sign on information, then open One Drive. You should see a few Excel programs. There is a COVID\_CHILL\_Assignment tool and a CHILL\_COVID\_Online\_Screening tool as well as Demo versions of each (to practice with).
2. Select "CHILL\_COVID\_Online\_Screening\_Log\_1.0," click on the 3 vertical dots next to the file title, select "Open" and then on "Open in app." If opening on a Mac, you will be given the option to enable macros. On a PC, you will have to manually enable macros once the file is open using the following steps:
  - a. Once the file is open, click on the "File" tab
  - b. Click on the "Enable Content" icon (upper left)
  - c. Click on "Advanced Options"
  - d. Select "Enable Content for this Session."
  - e. The programs should the work.
3. Go to "Sheet1" tab.
4. To enter a new patient and obtain a 3-digit study number and a 3-letter patient identifier, first ensure that the patient has not been previously screened by clicking on Sheet 1 and using the Excel find tool to check for the patient's MRN number.
5. If the patient has not been previously screened, click on "Sheet2" tab.
6. Push the "Push to Start" button. All cells should empty

7. Enter your name from the pulldown menu, the Patients name (Last, first), MRN number, Medical Unit (from the pulldown menu) and room number where they are currently located or are being immediately being transferred to.
8. If you know whether they are enrolled or excluded at this time, you can add this from the pulldown menu. If excluded indicate the reason from the pulldown menu. If multiple reasons, select “multiple exclusions” from the end of the pulldown menu. If you do not know the final status at this time, you can add it later. If you leave a required field empty the program will let you know.
9. Push the “Push button for study number and ID” button. The 3-digit number and 3-letter patient identifier are indicated in cells B14 and B15. Record them on the Screening/Enrollment/Randomization CRF. All data and date/time stamped are recorded on Sheet 1.
10. All data are automatically saved and the sheet locked so you just have to click on the close button.

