### 3.3/ Randomization

Subjects will be stratified by proning status at enrollment and randomized within each stratum to receive TH or usual temperature management using a 1:1 assignment ratio. Treatment group assignment will be made using an Excel-based assignment tool stored on the UMB Microsoft OneDrive, which records date, time, and investigator who makes the treatment assignment. Baseline APACHE II, Sequential Organ Failure (SOFA) score 3, driving pressure, P/F ratio, and oxygen saturation index will be documented at time of randomization to assess comparability of disease acuity between groups.

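### The plan does not show that the next assignment is concealed: the loaded assignments and the running log sit in the Excel workbook that enrolling staff open

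*Protocol*

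**What the plan says.** Protocol section 3.3 states that "Treatment group assignment will be made using an Excel-based assignment tool stored on the UMB Microsoft OneDrive", with patients "randomized within each stratum to receive TH or usual temperature management using a 1:1 assignment ratio". The strata are proning status, yes or no.

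The assignments do not come from a separate service. Section 2.2.1.2 says that a named individual "will oversee generation of random assignments into the computer-based CHILL assignment tool", and section 2.2.1.2.1 refers to prepared schedules against which a monthly list of stratum and arm, in date order, is checked.

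Section 3.3.2 gives the user's steps: open the workbook in the desktop application, enable macros, enter name, study ID, letter code and proning status, then press for the result. Step 9 reads: "The treatment assignment will be displayed in cell B12, all information will be entered along with date/time stamp on Sheet 2". Step 10 adds that data are saved and the sheet is locked. No hidden sheet, password, encryption, access right or block scheme is described.

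The coordinators' duties in section 2.3.3 include "Screening, enrollment, and randomization in all study units", and the same list has them obtaining consent. On masking, section 1.1 says: "Since the nature of the intervention precludes blinding".

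**The concern.** Concealment means that whoever decides on a patient's entry cannot know or predict the arm at that moment. Here the file opened for each draw is also the file into which the assignments were generated, and it holds the stratum-by-stratum history of earlier draws.

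There is some room to act on a prediction. Several exclusions in section 3.2.2 are judgements: whether the patient is moribund, whether intubation will last 48 h, whether the treating physician is willing. Proning status, which sets the stratum, is a care decision.

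Selection of this kind would distort the between-arm comparisons of SAEs and of 28-day VFDs, and no analysis can reliably remove it afterwards. The pilot is meant to settle whether COVID-19 patients enter the Phase IIb trial.

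**Working it through.** **Inputs.** Sample size: "We plan to randomize a total 20 patients over 4 months" (section 1.1). Ratio and strata: section 3.3, as above. Block size and stratum sizes are not stated, so fixed blocks of 2, 4 and 6 and splits of 10/10, 12/8, 16/4 and 20/0 are assumptions. The plan gives no predictability figure to reproduce.

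**Step 1: what the sheet lock implies.** The sentence about saving and locking is the same for the screening tool in section 3.1. There, staff are told to check for a previous screen by "clicking on Sheet 1 and using the Excel find tool", and to find forgotten IDs on that sheet. In this protocol's usage, then, a locked sheet can still be read. That does not prove that Sheet 2 of the assignment tool is readable, but it means the lock cannot be taken as concealment.

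**Step 2: guessing from past assignments.** The guesser names the arm with more places left in the current block. Expected correct guesses per full block:

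- Block of 2: 1/2 + 1 = 1.5, or 75%.
- Block of 4: 1/2 + 2/3 + 2/3 + 1 = 2.833, or 70.8%.
- Block of 6: 0.5 + 0.6 + 0.6 + 0.7 + 0.7 + 1 = 4.1, or 68.3%.

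A stratum of 10 ends part-way through a block of 4 or 6. For blocks of 4: 2 × 2.833 + 1/2 + 2/3 = 6.833 per stratum, or 13.67 of 20 over two strata. For blocks of 6: 4.1 + (0.5 + 0.6 + 0.6 + 0.7) = 6.5 per stratum, or 13.0 of 20.

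| Scheme (assumed) | Correct of 20, split 10/10 | Correct of 20, all splits | Certain in advance, all splits |
|---|---|---|---|
| Fixed blocks of 2 | 15.0 | 15.0 (75%) | 10.0 |
| Fixed blocks of 4 | 13.7 | 13.7 to 14.2 (68% to 71%) | 5.3 to 6.7 |
| Fixed blocks of 6 | 13.0 | 13.0 to 13.4 (65% to 67%) | 3.2 to 4.5 |
| Simple randomisation | 10.0 | 10.0 (50%) | 0 |

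The last column assumes that the block size has been worked out. If the unused list itself can be read, all future assignments are known under any scheme.

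**Step 3: a ceiling on VFD bias.** Suppose patients are steered so that expected VFDs are d higher when the guess is hypothermia and d lower when it is control, and the guess is right with probability g. The arm means shift by +(2g − 1)d and −(2g − 1)d, so the bias is 2(2g − 1)d:

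- g = 0.75: 1.00d
- g = 0.683: 0.73d
- g = 0.65: 0.60d

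The documents give no d. With d = 1 the ceiling is 0.6 to 1.0 VFDs; with d = 3 it is 1.8 to 3.0. A d of 3 means that the two kinds of steered patient differ by 6 VFDs.

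**Step 4: would varying the block size help?** With blocks of 4 and 6 mixed at random, two strata of 10, simulation gives a correct-guess rate of about 68%. Then 2(2 × 0.68 − 1)d = 0.72d, against 0.73d for fixed blocks of 4 and 0.60d for fixed blocks of 6. Fewer assignments are certain, but the guess rate is no lower.

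**The case against.** A reader might infer that staff can simply look up the next arm. The documents do not support that. Step 9 shows a display cell and a log, no step sends the user to Sheet 2, and nothing says that the unused list is visible. The screening log has to be searchable to catch duplicates, a need the assignment tool does not share. This objection stands, and it limits the point to concealment that is not shown.

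A reader might also infer that the log makes the next arm guessable. That needs restricted blocks, which the documents neither state nor exclude; under simple randomisation the log gives nothing away. This stands too.

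In an open, single-centre trial of 20, the team that randomises and completes the case report forms largely knows past assignments anyway. Removing the log alone would therefore change little. This is largely right, and it makes the unused list and any block scheme the more important things to protect.

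Finally, a reader might infer that staff may choose when to randomise within the 48 h window. Protocol section 5 does not say so: a patient who already meets the P/F criterion is randomised at enrolment, and otherwise the wait is set by a measured value. Exclusions and consent precede the draw, exclusion reasons are logged, and assignments are reconciled monthly. These narrow the room for selection, but the judgement-based exclusions keep some of it open. The separation of data and clinical cores described in section 2.3.1.3 does not address the workbook.

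**Conclusion.** The point holds as a weakness in the described procedure, not as a demonstrated breach. The plan places the loaded assignments and the cumulative log by stratum in a file that enrolling staff open, and names only a sheet lock as protection.

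The possible exposure runs from none (list hidden, simple randomisation: 50% correct guesses), through about 65% to 75% with fixed blocks of 2 to 6, to complete knowledge if the list is readable. The middle range rests on assumed block sizes and stratum splits.

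The VFD figures are ceilings: they assume that every patient can be steered on every guess and rest on an assumed d, so they do not carry the conclusion. The cooling part of the primary outcome is descriptive and essentially confined to the hypothermia arm. The comparisons mainly at risk are SAEs and the secondary clinical outcomes. The change is cheap and should be made.

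**What to change.** Amend section 3.3.2:

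1. The Data Management Core (DC) holds the unused assignments and the cumulative log where enrolling staff can neither open nor read them.
2. Staff receive one patient's assignment only after ID, letter code and proning status are irrevocably entered. The DC could release it, or the list and macro code could be password-encrypted. OneDrive permissions alone may not be enough, because a macro run by the user ordinarily has only the user's access. The correction note at the end of 3.3.2, which lets the user repeat the entry, must be brought into line.
3. In step 9, replace the reference to Sheet 2 with *in a log accessible only to the DC*.
4. Keep the monthly by-stratum list and the schedules in section 2.2.1.2.1 from anyone who enrols patients.
5. State any block scheme only in a document that enrolling staff do not see. Varying the block size is no substitute for items 1 and 2.

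The cost is a small rework of the workbook and a few sentences, and staff can no longer look up past assignments in it. If the list and Sheet 2 are already hidden, saying so and naming who has access would settle most of this.

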- Monitor for qualifying P/F ratio using the P/F ratio table. For each ventilator day, check the appropriate “Yes/No” box for PEEP $\geq$ 8 cm H2O, whether P/F $<$ 200, whether the value was calculated from the measured PaO2 (“M”) or imputed (“I”) from the SpO2. Record the value for the P/F ratio and the date and time it was measured. If patient meets all Berlin criteria, including P/F ratio  $<$  200 within 7 days of onset of intubation/mechanical ventilation, check the “Yes” box on line 14, collect the baseline blood sample, and proceed with randomization; otherwise, check the “No” box and STOP.
- If randomizing, record whether the patient is receiving intermittent prone positioning at the time of randomization on line 15.
- Obtain the treatment assignment using the on-line assignment tool, record the randomization date and time on line 16 and record the treatment assignment on line 17.
- For patients randomized to the cooling arm, initiate sedation, NMB, and cooling.

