**eTable 2: Imputed PF ratio (cells) for combinations of SpO2 (rows) and FiO2 (columns)**

	0.30	0.35	0.40	0.45	0.50	0.55	0.60	0.65	0.70	0.75	0.80	0.85	0.90	0.95	1.00
80%	148	127	111	98	89	81	74	68	63	59	55	52	49	47	44
81%	151	129	113	101	91	82	76	70	65	60	57	53	50	48	45
82%	155	132	116	103	93	84	77	71	66	62	58	55	52	49	46
83%	158	136	119	106	95	86	79	73	68	63	59	56	53	50	47
84%	162	139	122	108	97	89	81	75	70	65	61	57	54	51	49
85%	167	143	125	111	100	91	83	77	71	67	63	59	56	53	50
86%	171	147	129	114	103	94	86	79	73	69	64	61	57	54	51
87%	177	151	132	118	106	96	88	81	76	71	66	62	59	56	53
88%	182	156	137	121	109	99	91	84	78	73	68	64	61	58	55
89%	189	162	141	126	113	103	94	87	81	75	71	67	63	60	57
90%	196	168	147	130	117	107	98	90	84	78	73	69	65	62	59
91%	203	174	153	136	122	111	102	94	87	81	76	72	68	64	61
92%	213	182	159	142	128	116	106	98	91	85	80	75	71	67	64
93%	223	191	168	149	134	122	112	103	96	89	84	79	74	71	67
94%	236	202	177	157	142	129	118	109	101	94	89	83	79	75	71
95%	252	216	189	168	151	138	126	116	108	101	95	89	84	80	76
96%	273	234	205	182	164	149	136	126	117	109	102	96	91	86	82

Conditions required to use inferred P/F ratio include: (a) SpO2 values 80-96%, (b) SpO2 measured ≥10 min after FiO2 change, (c) PEEP ≥ 8 cm H2O, (d) adequate pulse oximeter wave form, and (e) qualifying inferred P/F ratio is confirmed 1-6 hrs after the initial determination.

P/F ratio criterion met within 7 ventilator days

- Yes Collect **baseline blood sample**, randomize and record randomization time and treatment assignment below
- No STOP

Is this patient currently receiving prone positioning alternating with supine positioning?

- Yes
- No

Randomization date/time:    /   /          
MONTH D D Y Y Y Y TIME (0-2400)

Treatment assignment (check one)

- Therapeutic Hypothermia
- Usual Treatment

Initiate sedation, NMB, and cooling protocol for subjects randomized to Therapeutic Hypothermia

Complete Baseline information CRF.

See schedule for first week blood and data collection below.

--	--

[figure not shown]
SITE ID

--	--	--	--

PATIENT ID

--	--	--

LETTER CODE

- Collect baseline blood and complete Baseline CRF based on 24h preceding randomization
- Collect day 1 blood and complete Day 1 CRF at 0800 on randomization day + 1; (the duration of day 1 may be 8h 1 min to 31h 59 min as indicated by the examples a - c)

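### The manual lets a user who has already seen the treatment assignment draw again when proning status was mis-entered; making the first assignment binding is a cheap, minor safeguard.

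*Protocol*

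**What the plan says.** Protocol Section 3.3 stratifies by proning status and randomizes 1:1 within each stratum with an Excel tool. In Section 3.3.2, step 8 has the user enter and confirm proning status. Step 9 follows: "The treatment assignment will be displayed in cell B12, all information will be entered along with date/time stamp on Sheet 2". Step 10 adds: "All data are automatically saved and the sheet locked so you just have to click on the close button".

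The closing paragraph of Section 3.3.2 deals with mistakes. Its general sentence has lost a verb, "make sure you the correct treatment assignment right away", and does not settle which assignment stands. Two specific rules follow:

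- Wrong proning status: "If you put in the wrong proning status, repeat with correct status and let me know so I can fix the error".
- Wrong identifier: "If you entered wrong patient number or 3-letter code, use the treatment assignment provided and let me know so I can fix the error".

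On the screening form, Section 10.1 has staff "record whether the patient is receiving intermittent prone positioning at the time of randomization on line 15", and the next instruction is "Obtain the treatment assignment using the on-line assignment tool, record the randomization date and time on line 16". Line 15 of the form itself asks: "Is this patient currently receiving prone positioning alternating with supine positioning".

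**The concern.** Once an arm has been seen, it should not be replaceable by the person who saw it. Here the user sees the arm, declares the stratum entry wrong, draws again alone and gives notice afterwards. No release is needed before the second draw. Section 1.1 says that blinding is not possible, and Section 2.3.3 gives the coordinator team screening, enrollment and randomization together. The person drawing may therefore know both how sick the patient is and which arm came up.

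Safety is part of the primary outcome (Section 1.1), and the SAP compares SAEs and 28-day ventilator-free days between arms. Those comparisons depend on sound allocation. The cooling outcomes (time to target, percent of time in range) are descriptive in the SAP and are much less exposed.

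**Working it through.** The plan has no figure to reproduce: it states 20 patients, 1:1, two strata, and gives no block size, stratum share or error rate. The check is a reading of the procedure plus illustrations on stated assumptions.

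**1. What prevents a redraw and what only detects it.**

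- *Tool log* (Sections 2.2.1.2, 3.3 and 3.3.2): records date, time and user. Detects.
- *Sheet lock* (step 10): protects what was saved. The repeat instruction presupposes that the tool can be run again.
- *Form line 15* (Section 10.1 and the source document): completed before the assignment is obtained, so a false correction would contradict it. Detects.
- *Monthly list* of stratum and assignment, checked against schedules and site documents (Section 2.2.1.2.1): detects.
- *Baseline Data CRF line 32* and *Summary of Patient Outcomes line 14*: completed after randomization. Weak detection.

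None of these requires release before a second draw. Section 3.3.2 does not say whether both log rows survive the correction, or what happens to the displaced slot on the list.

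**2. Honest errors.** Assume separate 1:1 lists per stratum. If a share e of entries is wrong and always redrawn, P(either arm) = (1 − e)(0.5) + e(0.5) = 0.50 for any e.

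**3. Arm-dependent redraws.** If a share f of unwanted first assignments is redrawn once, P(preferred arm) = 0.5 + 0.5 × f × 0.5 = 0.5 + 0.25f. Assumed f of 0.1, 0.25, 0.5 and 1 gives 0.525, 0.5625, 0.625 and 0.75. The last value is a ceiling that needs every unwanted assignment to be redrawn.

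**4. Size of a deliberate, severity-targeted misuse (illustration only).** Take severity as standard normal, with a redraw made with probability q when the first draw is hypothermia and severity is above zero. Expected redraws are 20 × 0.5 × 0.5 × q = 5q, and half of them change the arm. A switched patient has mean severity √(2/π) = 0.80, so each switch moves the arm difference by about 2 × 0.80/10 = 0.16 SD. Simulation (200,000 trials) agrees:

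| q | redraws per trial | patients switched | shift (SD) |
|---|---|---|---|
| 0.1 | 0.50 | 0.25 | 0.040 |
| 0.2 | 1.00 | 0.50 | 0.079 |
| 0.4 | 2.00 | 1.00 | 0.162 |

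The chance SD of the difference with 10 per arm is √(1/10 + 1/10) = 0.447.

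**5. What a binding first draw costs in balance.** Assume one mis-entry per 20 patients and permuted blocks within strata (12,000 trials per cell, Monte Carlo SE about 0.01). Entries are keep first draw / redraw with slot used up / redraw with slot restored.

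| Share in one stratum | Block | Summed within-stratum arm difference | Overall arm difference |
|---|---|---|---|
| 50% | 2 | 1.94 / 1.46 / 0.99 | 0.49 / 0.95 / 0.50 |
| 50% | 4 | 2.10 / 1.69 / 1.33 | 0.78 / 1.09 / 0.77 |
| 50% | 6 | 2.22 / 1.88 / 1.63 | 1.04 / 1.25 / 1.06 |
| 25% | 2 | 1.90 / 1.43 / 1.00 | 0.50 / 0.93 / 0.51 |
| 25% | 4 | 2.06 / 1.64 / 1.34 | 0.77 / 1.07 / 0.79 |
| 25% | 6 | 2.22 / 1.83 / 1.61 | 1.08 / 1.22 / 1.05 |

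Keeping the first draw costs 0.3 to 0.5 patients within strata against a used-up slot, and 0.6 to 1.0 against a restored one. A restored slot, however, is already known to staff before the next patient in that stratum. Overall balance is better than with a used-up slot and within 0.03 patients of a restored one.

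**6. Time point of the stratum (a separate matter).** Section 3.3 takes proning status at enrollment. Section 10.1, form line 15 and the Outcomes form take it at randomization or as current. Step 8 gives no time. Under Section 5, patients who already meet the P/F criterion are enrolled and randomized together, so the difference matters only for those randomized later whose proning has changed. Section 5 also numbers the form differently: randomization yes/no, date and assignment are on lines 12, 14 and 15 there, but on lines 14, 16 and 17 of the form, where line 15 is proning.

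**The case against.** The current rule is coherent. Repeating with the true status gives the patient an arm from the correct stratum list, which is the allocation that Section 3.3 promises, and an honest redraw is unbiased. A reader might infer that the two error rules contradict each other. They do not: a wrong identifier leaves the stratum right, so keeping the arm there also respects the true list. Keeping a wrong-list draw does loosen within-stratum balance after every honest error. All of this stands.

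Misuse would also be fairly easy to find. Twenty patients over four months is about five entries a month to check, and a false correction would conflict with line 15. The data core works to its own procedures, which are not among the documents, so log retention and displaced slots may be covered there. This too stands, and it is why the point is minor. It does not change the fact that the manual itself permits the second draw and asks only for notice afterwards.

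A wording change alone would not stop someone determined to redraw. That is correct: without a block in the tool, a deliberate second draw would still come to light only through the log and the monthly check.

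**Conclusion.** A cheap improvement of minor weight. The manual allows a seen assignment to be replaced on the user's own statement, and the existing controls detect this rather than prevent it. No misuse is shown. The expected bias cannot be estimated, because the documents give no mis-entry or misuse rate, and it is probably small. A reader might take the 0.75 in step 3 as the expected allocation, or conclude that the trial's allocation is biased. The documents support neither: 0.75 describes systematic misconduct, and even the largest illustrated severity shift (0.16 SD) is about a third of the chance SD (0.162/0.447 = 0.36).

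The balance cost of the remedy, about 0.3 to 1.0 patients within strata per mis-entry, rests on assumed block sizes and stratum shares. The SAP names no analysis by proning, and overall balance is essentially no worse, so the trade favors a binding first assignment. The time-point mismatch is a separate inconsistency and adds no evidence of misuse.

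**What to change.** In Section 3.3.2, replace the proning sentence with: *If the wrong proning status was entered, keep the first treatment assignment displayed, do not run the tool again, and report the error.* Adapt the sentence before it so that it names the first assignment displayed. State that the log row stays unaltered and that the true proning status is recorded separately. If any analysis by proning is added, it should use the true status.

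This removes the permitted redraw and makes any second draw a plain protocol deviation. To block a second draw, the tool must also refuse a repeated study ID unless the data core, which oversees the tool (Section 2.1.2.1.1), releases it. That step is optional. Its cost is that a patient whose ID was used in error must wait for release, so the data core would need an out-of-hours contact.

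Separately, settle on one time point for proning status in Section 3.3, step 8 and the forms, recorded on the Screening/Enrollment/Randomization form before the draw, and correct the line numbers in Section 5.

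The cost is two sentences, one agreed time point and some renumbering, plus the looser within-stratum balance shown above.
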